1.3. Primary Efficacy Objective

The primary efficacy endpoint of the study is the composite of BK Virus infection, including viruria > 500 copies, viremia > 500 copies, or nephropathy as defined by Banff classification (sv 40 positivity with or without tubulitis or if/ta).

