3.1. Description of Study Design

This will be a single center prospective case control study. We expect 40% of patients will develop BK viruria, 20% BK viremia, 5% BK viral nephropathy (BKVN). Patients will be managed using standard of care for our center (thymoglobulin induction, tacrolimus/mycophenolate/prednisone). Target tacrolimus level is 8-12 ng/mL for the first 6 months post transplant and 6-9 ng/mL thereafter. BK urine/serum is routinely monitored during the first year post transplant. A population of 100 patients is calculated to show significant difference for p value < 0.05.

Population:

Study Group: Post transplant patients (kidney transplant alone) with standard of care immunosuppression, no prior rejection, prior BK or opportunistic infection, and negative BK screening at post-transplant month 1, who have a tacrolimus concentration/dose of < 1 and a steady state therapeutic level will be eligible. Patients who consent to participate will be converted to Envarsus at 20% reduction in tacrolimus dose.

Control Group: Post transplant patients (kidney transplant alone performed between 10-2016 and time of consideration for study control group) with standard of care immunosuppression, no prior rejection, prior BK or opportunistic infection, who had a negative BK screening at post-transplant month 1 and tacrolimus concentration/dose of < 1 at post-transplant month 1, and BK data available for months 2, 3, 6, 9, 12 post transplant.

Study visits: Post-transplant Months 2, 3, 6, 9, 12

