11.7. Reporting of Other Safety Information

An investigator shall notify the site IRB according to the site's IRB guidelines when an "unanticipated problem involving risks to participants or others" is identified, which is not otherwise reportable as an adverse event.

12. Statistical Considerations and Analytical Plan

This is a single center prospective study comparing incidence of BK infection in rapid metabolizers converted from tacrolimus to Envarsus against a recent historical control of rapidly metabolizing recipients who had BK screening at similar points, but remained on tacrolimus.

This study has both safety and efficacy endpoints.

We will use standard descriptive statistics for continuous and categorical data to define adverse events, and clinical outcomes as noted above. Analysis will be undertaken utilizing UAB statistical support in the School of Public Health and Transplant Quality, Informatics and Outcomes.

The enrollment plan is based on a power calculation. A population of 100 patients is calculated

to show significant difference for p value < 0.05.

Our results will be submitted to national/international nephrology/transplant meetings, and as a primary manuscript reporting the primary efficacy and safety data, and secondary manuscripts reporting different secondary endpoints, as appropriate.

We expect the changes over time in these assays to be approximately linear. If after examination of the data, this appears to not be the case, then we will either transform the assay measures or model the time axis time points as an unordered factor (similar to repeated measures ANOVA, but without the requirement for fully balanced data).

We will use descriptive analyses to summarize subject characteristics of our study population. Dichotomous variables will be summarized as proportions with 95% confidence intervals. Continuous variables will be summarized using means, standard deviations, and 95% confidence intervals if they are symmetric and unimodal. Otherwise, they will be summarized using the median and the interquartile range. Simple t-, chi-squared, or Fisher's exact test, as appropriate, will be used to compare quantitative measures across treatment groups. The following variables will be summarized:

- Baseline and demographic characteristics
- Use of concomitant medications
- Reasons for early termination
- All reportable AEs

No formal interim analyses of this study are planned.

13. Identification and Access to Source Data

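### Treatment group largely follows calendar period and Section 12 plans no calendar-time analysis, so a drift in the centre's BK rate could pass for, or hide, an Envarsus effect

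*Combined protocol and SAP*

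**What the plan says.** Section 3.1 defines the control group by chart criteria, with transplant dates given as "kidney transplant alone performed between 10-2016 and time of consideration for study control group". Controls must also have a negative month-1 BK screen, a month-1 tacrolimus concentration/dose (C/D) ratio below 1, and BK data at months 2, 3, 6, 9 and 12. For the study group the same section says "Patients who consent to participate will be converted to Envarsus at 20% reduction in tacrolimus dose". There is no randomisation and no concurrent arm.

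Section 12 describes the comparison as being "against a recent historical control of rapidly metabolizing recipients who had BK screening at similar points, but remained on tacrolimus". For comparing groups it names t, chi-squared or Fisher tests. It also promises summaries of baseline characteristics and concomitant medication. Its sentence on approximately linear change concerns assay values over time, not transplant date.

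The primary endpoint (Section 1.3) is the "composite of BK Virus infection, including viruria > 500 copies, viremia > 500 copies, or nephropathy as defined by Banff classification". Section 3.1 also notes that "BK urine/serum is routinely monitored during the first year post transplant".

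**The concern.** Controls must already have a year of BK results when they are chosen, while study patients enter by 8 weeks after transplant. This pushes controls towards earlier transplants. Anything that changes at the centre between the two periods then acts on the comparison exactly as a drug effect would. Examples are the BK assay, the response to a positive test, mycophenolate dosing and donor mix.

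The protocol gives reasons to take this seriously. Section 2.1.1 names degree of immunosuppression as the most consistent BK risk factor. Section 6.1.2 leaves mycophenolate dose to investigator discretion after entry, and Section 6.2 leaves prophylaxis to standard of care.

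At stake is the trial's main claim, that conversion lowers BK infection. A downward drift could produce that claim without any drug effect, and an upward drift could mask a real one. More controls do not help: they raise precision and leave the bias as it is.

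**Working it through.** **Inputs.** Section 3.1 expects viruria in 40%, viremia in 20% and nephropathy in 5%. No composite rate is given. I take 40% (viremia and nephropathy nested within viruria) and vary it. The significance level is 0.05, with sidedness not stated; I assume two-sided, so 2.5% is nominal for a result favouring Envarsus. Drift sizes of 5, 10 and 15 points are assumptions.

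**The plan's own figure.** Section 3.1 says "A population of 100 patients is calculated to show significant difference for p value < 0.05". This cannot be reproduced, because effect size, power and allocation are not given, nor whether 100 is the total, the number per group or the Envarsus group alone. With n per group = [1.96√(2p̄q̄) + z_power√(p₁q₁+p₂q₂)]²/d²:
- 40% v 12% at 90% power: (1.2158 + 0.7534)²/0.0784 = 49.5, so 50 per group and 100 in total. This is one of several fits.
- 40% v 20% at 80% power: (1.2702 + 0.5323)²/0.04 = 81.2, so 82 per group and 164 in total.

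I therefore show both 50+50 and 100+100.

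**Chance that drift alone favours Envarsus.** Approximately Φ[(d − 1.96√(2p̄q̄/n)) / √((p₁q₁+p₂q₂)/n)]. For a fall from 40% to 30%:
- n = 50: (0.10 − 0.1870)/0.0949 = −0.917, giving 18.0%.
- n = 100: (0.10 − 0.1322)/0.0671 = −0.480, giving 31.6%.

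Exact binomial enumeration, counting only results that favour Envarsus:

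| Fall, no drug effect | 50+50 chi-squared | 50+50 Fisher | 100+100 chi-squared | 100+100 Fisher |
|---|---|---|---|---|
| 0 points | 2.6% | 1.6% | 2.6% | 1.8% |
| 5 points | 7.5% | 5.0% | 10.9% | 8.4% |
| 10 points | 17.9% | 13.1% | 31.6% | 26.3% |
| 15 points | 35.8% | 28.6% | 62.6% | 56.4% |

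An even chance of a false benefit needs a fall of about 18 points (50+50) or 13 points (100+100).

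**Other composite rates.** If the components were independent, the composite would be 1 − 0.60×0.80×0.95 = 54%; if disjoint, 65%. A 10-point fall then gives about 17% at 50+50, and 29% to 30% at 100+100.

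**Upward drift.** Take a true effect of 40% to 20% and a 10-point rise, so that the study group shows 30%. Power falls from 60% to 18% (50+50) or from 88% to 32% (100+100).

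**Can the controls alone show drift?** I simulated rates of 40%, 35% and 30% in three equal control periods. A trend test detects this with about 9% power for 50 controls and 14% for 100.

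**What a reference cohort buys and costs.** With a 10-point drift, no drug effect and 50+50, subtracting the change seen in a reference cohort on tacrolimus reduces false benefit from 18%. It becomes about 3% if the full drift is shared, and 6% to 8% if half is shared (simulation, 50 to 200 reference patients per window). The 95% half-width at 40% v 30% is 1.96√(0.24/50 + 0.21/50) = 18.6 points. Adding reference cells at the same two rates, it becomes 1.96√(0.009 + 0.009) = 26.3 points with 50 per window, or 1.96√(0.009 + 0.00225) = 20.8 points with 200 per window.

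**The case against.** The historical control is openly declared, and both groups share much: one centre, the same standard-of-care wording, the same month-1 BK and C/D criteria, and the same BK testing months. The planned summaries of baseline characteristics and concomitant medication may expose a shift in, for example, mycophenolate use. Donor mix, induction and entry mycophenolate dose could also be adjusted for at patient level. All this stands and narrows the concern. It does not reach assay changes or the response to a positive test, and none of it looks at the BK rate itself.

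A reader might infer that a modest fall would be declared a drug effect. The figures do not support that: with 50 per group, a fall of 5 to 10 points is not declared a benefit in about 82% to 92% of trials. A reader might also infer that group and period are completely confounded. The control window runs up to the time each control is considered, so overlap is permitted, though nothing requires or uses it.

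A further objection concerns the reference cohort. Subtracting the change in patients with C/D of 1 or more assumes that they share the drift. Section 2.3.2 reports BK viremia of 8% in fast and 1% in slow metabolisers (slow there meaning above 1.55), so an absolute change may not carry over. The documents also do not say how ineligible recipients are managed during the study. These points limit the analysis to qualifying the conclusion; they do not remove its value.

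**Conclusion.** The point holds in this form: group largely follows calendar period, no calendar-time analysis is planned, and drift could be mistaken for an Envarsus effect or conceal one. The bias in the estimate equals the drift, whether or not the test is significant. For an assumed 10-point fall, the chance of a false benefit rises from 2.5% nominal to about 18% (50+50) or 32% (100+100), somewhat less with Fisher's test.

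These figures rest on a 40% composite rate, a two-sided 5% level, the two group sizes shown and assumed drifts. The documents show neither that drift has occurred at this centre nor its direction. The gap is worth closing because the first steps use data that the control criteria already require.

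**What to change.** Add to Section 12, as prespecified sensitivity analyses:

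1. Report the control BK composite by transplant year with 95% confidence intervals, descriptively. Say that a non-significant trend will not be read as proof of no drift. Repeat the primary comparison adjusting for transplant date, or restricted to the most recent controls. Report how far the two groups' dates overlap, since adjustment without overlap is extrapolation.
2. State the drift that would remove the result. For significance, this is roughly the confidence limit of the difference nearest zero. For example, 40% v 12% with 50 per group gives 28 ± 1.96√(0.24/50 + 0.1056/50) = 28 ± 16.3 points, so a drift of about 12 points would suffice.
3. Where routine BK results can be abstracted, take recipients with a negative month-1 BK screen and C/D of 1 or more who remained on tacrolimus, in the same two calendar windows. Compute the change in the composite between windows. Report the Envarsus–control difference with and without that change, on both the absolute and the ratio scale. State the assumption that drift is similar in both metaboliser groups. Use the result to qualify the conclusion, not as a pass/fail gate.

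Cost: items 1 and 2 need only analysis time. Item 3 needs chart abstraction with IRB cover, and widens the interval at 50+50 from about ±18 or 19 points to about ±21 to ±26. Eligibility, treatment and visits are unchanged.

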2.4 Clinical Studies of Envarsus

2.4.1

Data from a randomized, double blinded study of Envarsus versus tacrolimus by Budde⁵ and data from the open label phase III MELT Trial both demonstrated non inferiority of Envarsus.

In the phase III RCT by Budde, de novo kidney transplant patients were placed on

tacrolimus vs Envarsus along with mycophenolate mofetil (MMF) and prednisone and followed for endpoints of death, graft failure, or biopsy proven rejection. At 12 months, overall survival was 97% in both Envarsus and tacrolimus recipients; graft survival was 97 and 96%, respectively, and graft and patient survival combined was 94 % in both groups. The incidence of clinically suspected and treated rejection was 14 versus 16% in Envarsus versus tacrolimus recipients, and no significant treatment differences were found in the number of biopsy-proven acute rejection episodes. A total of 195 Envarsus and 199 tacrolimus recipients completed 24 months of follow-up on their assigned treatment. At 24 months, the treatment failure rate was 23.1 versus 27.3 %, respectively, with a treatment difference of 4.14 (95 % CI 11.38 to +3.17), again demonstrating noninferiority. The incidence of the individual events comprising treatment failure were similar between treatment groups at 24 months: biopsy-proven acute rejection occurred in 17.2 % of Envarsus and 18.2 % of tacrolimus recipients, graft failure in 4.1 and 5.5 %, respectively, death in 4.1 and 4.7 %, and lost to follow-up in 1.5 and 2.9 %. Renal function was also similar between treatment groups over the 24month period. The total daily tacrolimus dose was 25 % lower in Envarsus than in tacrolimus recipients in the second year of treatment; Ctrough values remained similar.

2.4.2

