3.4. Secondary Efficacy Endpoints

The secondary end-points to evaluate the effect of Envarsus conversion will

include: incidence of rejection, graft failure, graft dysfunction as defined by a 15% decrease in estimated glomerular filtration rate (eGFR), and proteinuria.

4. Rationale for Study Population

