4.1. Enrollment Eligibility Criteria

4.1.1. Inclusion Criteria

Individuals who meet all of the following criteria are eligible for enrollment as study participants:

- 1. Patient must be able to understand and provide informed consent
- 2. Age \geq 18 years of age at the time of study entry
- 3. Recipient of a deceased or living donor kidney transplantation
- Maintenance immunosuppression consisting of tacrolimus/MMF/MPA (≥1000 mg/720 mg daily) ± prednisone (≤10 mg/day)
- 5. Patient is less than or at 8 weeks post transplant with a negative serum BK Virus screen at 3-4 weeks post transplant
- 6. Patient has a tacrolimus drug dose/concentration of > 1 with therapeutic tacrolimus levels.
- 7. Women of childbearing potential defined as all women physiologically capable of becoming pregnant, must have reviewed Mycophenolate REMS and have a negative pregnancy test upon study entry.
- 8. Female (and male) subjects with reproductive potential must agree to use a highly effective method of birth control for the duration of the study. Please note that according to the US product information for MMF/MPA, two reliable forms of contraception must be used simultaneously unless female sterilization, male sterilization, post-menopausal status or total abstinence is the chosen method.

Acceptable methods of highly effective birth control include:

- Condom with spermicide
- Diaphragm and sperm ide
- Cervical cap and spermicide
- Use of oral, injected or implanted hormonal methods of contraception or other forms of hormonal contraception that have comparable efficacy (failure rate <1%), for example hormone vaginal ring or transdermal hormone contraction
- Intrauterine device (IUD)

Female sterilization (have had surgical bilateral oophorectomy with or without hysterectomy) or tubal ligation at least six weeks prior to screening.

Male sterilization at least 6 months prior to screening. For female subjects on the study, the vasectomized male partner should be the sole partner for that subject.

Post menopausal women defined as being not of child bearing potential if they have had 12 months of natural (spontaneous) amenorrhea.

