9.1. Enrollment

The research study will be explained in lay terms to each potential research participant. The potential participant will sign an informed consent form before undergoing any study procedures. A participant is considered enrolled in the trial once the consent form has been signed.

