9.4. Visit Time Frames/ Windows

Study visits should take place within the time frames specified below in Table 1. The designated visit windows for each scheduled study visit are indicated in Appendix 1 Schedule of Events.

Visit No.	Study Visit Label	Time Frame Post Transplant
Screen	Study Eligibility	Approximately 1 month
1	Enrollment Day 0/ Visit 1	Approximately 2 months
2	Study Day 30/ Visit 2	Approximately 3 months
3	Study Day 120/ Visit 3	Approximately 6 months
4	Study Day 210/ Visit 4	Approximately 9 months
5	Study Day 300/ Visit 5	Approximately 12 months

10. Criteria for Participant Completion and Premature Study Termination

Participants may be prematurely terminated from the study for the following reasons:

- The participant elects to withdraw consent from all future study activities, including follow-up.
- The participant is "lost to follow-up" 3 months after the date of a missed study visit (i.e., no further follow-up is possible because attempts to reestablish contact with the participant have failed).
- The participant dies.
- The Investigator no longer believes participation is in the best interest of the participant.
- CTCAE Grade 3 or higher drug-related reaction
- A decision is made by the investigators and/or study supporter to stop the study

11. Safety Monitoring and Reporting

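### Controls must have BK results through month 12 to qualify, so they are selected on events after baseline; study patients enter by about month 2 with no such condition.

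*Combined protocol and SAP*

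**What the plan says.** **Controls.** Section 3.1 describes chart-identified kidney recipients "who had a negative BK screening at post-transplant month 1 and tacrolimus concentration/dose of < 1 at post-transplant month 1". The same sentence then sets a condition on later follow-up: "and BK data available for months 2, 3, 6, 9, 12 post transplant". Section 12 calls them a "recent historical control of rapidly metabolizing recipients who had BK screening at similar points, but remained on tacrolimus".

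**Study group.** Section 3.1 and the lists in 4.1.1 and 4.1.2 use only facts known at entry. Timing is fixed by inclusion criterion 5: "Patient is less than or at 8 weeks post transplant with a negative serum BK Virus screen at 3-4 weeks post transplant". Section 9.1 adds: "A participant is considered enrolled in the trial once the consent form has been signed". Table 1 (section 9.4) puts enrollment at about 2 months. No later BK result is needed to be eligible.

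**After enrollment.** Section 10 lists reasons for early termination, including withdrawal, loss to follow-up and "The participant dies".

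**Endpoints and analysis.** The primary efficacy endpoint is the BK composite (3.3). The secondary endpoints include "incidence of rejection, graft failure, graft dysfunction as defined by a 15% decrease" in eGFR, and proteinuria (3.4). Section 12 plans simple t-, chi-squared or Fisher tests and a summary of reasons for early termination. It defines no analysis set, gives no rule for incomplete BK data, and plans no adjustment or sensitivity analysis for how controls were chosen.

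**The concern.** One group is defined by what is known at entry, the other partly by what happened over the following ten months. A study patient who dies, leaves or misses tests is in the trial and drops out of it. A control with the same course never appears. The comparison is not randomized, so the definition of a control carries the inference.

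Two kinds of outcome are exposed:

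- **Death and graft failure.** Controls cannot die before the month-12 test. Graft failure is probably undercounted as well, though this is an inference, because BK testing can continue after graft loss. With no true drug effect, Envarsus would look worse. Death is not a secondary endpoint, but graft failure is, and a fatal infection is a Grade 5 event (11.3.1) within the primary safety endpoint (3.2).
- **The BK composite.** Bias arises if having complete tests is related to BK risk. Losing controls who did badly could remove BK cases. Closer testing of BK-positive patients could enrich for them. The plan gives no means of telling which.

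If staying on tacrolimus (section 12) is applied over the whole 12 months, it is a second condition of the same kind. The documents do not say.

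**Working it through.** **1. Rules side by side**

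| | Control | Study patient |
|---|---|---|
| Baseline BK condition | negative screen at month 1 | negative serum screen at weeks 3-4; serum BK below 500 copies/mL at entry (4.1.2) |
| Counted from | after month 12, once all tests exist | consent, by about month 2 |
| Later BK results required | months 2, 3, 6, 9, 12 | none |
| Death before month 12 | cannot qualify | terminated after enrollment |

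Month 2 is the study group's own entry visit, so the follow-up condition differs mainly at the four tests in months 3, 6, 9 and 12.

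**2. Inputs**

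- BK rate 40%: the expected viruria rate in 3.1, used here for the composite in both groups with no drug effect.
- 50 per group: an assumption. Section 3.1 gives only 100 patients and p < 0.05. Power, effect size, sidedness and allocation are not stated, so the 100 cannot be reproduced. The point does not depend on it.
- Share of controls removed (*d*) and their BK risk (*r*): assumptions.

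**3. Death or graft loss.** Section 2.4.1 reports that "graft and patient survival combined was 94 % in both groups" at 12 months. That is 6% with an event, counted from transplant, so it is an upper guide for the period from month 2. Assuming 2% to 6%, the expected study-group count is 50 × 0.02 = 1 to 50 × 0.06 = 3. Controls would have no deaths and probably fewer graft losses.

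**4. BK composite.** Control rate after selection = (0.40 − *d* × *r*) / (1 − *d*). Rejection is for an uncorrected two-sided 5% chi-squared test, by exact enumeration, with the study rate at 40% and control rates rounded to three decimals. Unrounded rates change the results by at most 0.1 point.

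| *d* | *r* | Control rate | Rejects | Favoring Envarsus |
|---|---|---|---|---|
| 0 | – | 40.0% | 5.2% | 2.6% |
| 6% | 100% | 36.2% | 6.9% | 1.0% |
| 6% | 60% | 38.7% | 5.4% | 1.9% |
| 6% | 20% | 41.3% | 5.5% | 3.6% |
| 6% | 0% | 42.6% | 6.2% | 4.8% |
| 10% | 100% | 33.3% | 10.7% | 0.4% |
| 10% | 60% | 37.8% | 5.8% | 1.5% |
| 10% | 20% | 42.2% | 5.9% | 4.4% |
| 10% | 0% | 44.4% | 7.8% | 6.9% |

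If only half of the expected 5% with BK nephropathy were removed: (0.40 − 0.025) / 0.975 = 38.5%, with rejection 5.5%.

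**5. Missed tests.** Suppose each of the four later tests is present independently with probability 0.95 or 0.90 (assumption). The share dropped is 1 − 0.95⁴ = 18.5% or 1 − 0.90⁴ = 34.4%. Null relative risk = 0.40 / control rate.

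| Dropped | *r* | Control rate | Null relative risk |
|---|---|---|---|
| 18.5% | 60% | 35.4% | 1.13 |
| 18.5% | 20% | 44.6% | 0.90 |
| 34.4% | 60% | 29.5% | 1.36 |
| 34.4% | 20% | 50.5% | 0.79 |

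With *r* = 40% the control rate stays at 40% and the relative risk at 1.00. Selection does no harm to this endpoint if completeness is unrelated to BK risk.

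**The case against.** The difference in the rules is plain from the text. The case on the other side is about size and remedy.

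- **Size.** The larger rejection rates need every removed control to have BK, or none. With a BK risk of 20% to 60% in those removed, 6% or 10% removal gives only 5.4% to 5.9%. Section 3.1 says BK is monitored routinely in the first year, so few controls may be lost. Deaths and transfers remove tests in blocks, so the independent-miss scenario is only illustrative. This stands as a limit on the figures. But no completeness rate is given, and one missing result out of five disqualifies a control.
- **Direction.** Where removed controls are mostly BK cases, the excess false positives run against Envarsus. This is correct and is shown in the working. Removal of mostly BK-free controls runs the other way.
- **Purpose.** The required months match the study visits, which equalizes the chances of detecting BK. Dropping the rule while keeping a simple proportion test would let less-tested controls look BK-free. This stands, and is why the deletion has to come with a time-to-event analysis. That analysis has limits of its own: events are seen only at visits up to three months apart, and censoring at the last test assumes that dropout is uninformative.
- **A lighter repair** would be to report the exclusions, apply one missing-data rule and add a sensitivity analysis. It would leave the main comparison resting on controls selected by their follow-up.
- **Month 2.** Section 4.1.2 excludes study patients with serum BK of 500 copies/mL or more at entry, while controls need only a negative month-1 screen. This is a separate difference and would favor Envarsus. A shared landmark with the same entry criteria removes it too.

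**Conclusion.** The concern holds. Followed as written, the plan selects controls on survival and complete follow-up to month 12 and does not select study patients that way. The planned tests do not correct this.

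The absence of control deaths before the month-12 test is certain. Undercounting of control graft failures is probable, on a scale of 1 to 3 study-group deaths or graft losses per 50 if the month 2-12 risk is 2% to 6%. For the BK composite neither direction nor size can be determined from the documents. The effect may be negligible (false-positive rate 5.4% to 5.9% under moderate assumptions) or material (7.8% to 10.7% with 10% removed at the extremes, more if many controls miss a test). All of these rest on an assumed 50 per group, a 40% rate in both groups, and assumed removal shares and risks. The change should be made because the flaw is certain and the remedy is cheap if it comes before controls are selected.

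**What to change.** 1. Delete the requirement for BK data at months 2 to 12. Take all consecutive recipients from the stated period who meet the entry criteria at a common landmark of about month 2, the study group's time zero. These criteria include being on tacrolimus and the same BK entry criterion as study patients. Set no condition on anything later, and state that staying on tacrolimus after the landmark is not required.
2. In both groups analyze time from the landmark to first BK event, censoring at the last BK test and treating death and graft loss as competing events. Count graft failure and death from the same landmark.
3. State that all converted patients are analyzed in the Envarsus group, and that routine BK results are abstracted to month 12 for everyone who has not withdrawn consent, so that follow-up rules match.
4. Report how many otherwise eligible controls lack each scheduled test.

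**Cost.** Protocol and SAP wording, and chart abstraction for controls with incomplete testing, done before controls are selected. No new patients, visits or procedures are needed. The price is the extra abstraction and some censored control data.
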